6.3 Derivation variables

1) Survival time analysis

It is defined as follows:

Endpoint	Start date	End date (event)	End date (censor)
Real-world PFS	Date treatment with avelumab and/or axitinib was initiated (if not on the same day, whichever occurs earlier)	Date of first disease progression (clinical evaluation based on radiological, laboratory, pathological, or other evaluation by the principal investigator) or death from any cause, whichever occurs earlier	Date of last confirmation of progression-free survival or start of subsequent treatment (whichever occurs earlier)
TTF of avelumab and axitinib	Date treatment with avelumab and/or axitinib was initiated	Date of completion of treatment with avelumab and/or axitinib	Date of last confirmation of progression-free survival or date of last dose in case of efficacy stopping (whichever date occurs earlier)
TTF of avelumab	Date treatment with avelumab was initiated	Date of completion of treatment with avelumab	Date of last confirmation of progression-free survival or date of last dose in case of efficacy stopping (whichever date occurs earlier)
TTF of axitinib	Date treatment with axitinib was initiated	Date of completion of treatment with axitinib	Date of last confirmation of progression-free survival or date of last dose in case of efficacy stopping (whichever date occurs earlier)

2) Objective response rate

ORR is defined as the proportion of patients with a CR or PR as the best overall response in tumor assessment during the observation period, as assessed by an investigator under actual clinical practice, including assessment based on RECIST ver. 1.1.

3) Calculation of duration

Duration	Definition
Duration of avelumab treatment	Date of last dose – date of initial dose + 14
Duration of axitinib treatment	Date of last dose – date of initial dose + 1
Duration of non-administration	Date of end – Date of start + 1

4) Corticosteroid equivalent dose (prednisolone equivalent)

This will be calculated as shown in the table below.

Generic name	Corresponding amount (mg)	Prednisolone conversion ratio
Cortisone	25	0.2
Hydrocortisone	20	0.25
Prednisolone	5	1
Methylprednisolone	4	1.25
Triamcinolone	4	1.25
Dexamethasone	0.75	6.7
Betamethasone	0.6	8.3

5) Date of initial dose

If avelumab and axitinib are administered for different durations, the earlier of the two dates should be used as the date of the initial dose.

6) Date of last confirmation of progression-free survival

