8.3.2 Continuation of first-line treatment

Analysis set	Analysis population
Details of analysis	Tabulate the duration of treatment (months), DI, dosing status, and reason for interruption, dose change, or discontinuation of avelumab and axitinib.
Definition	
• Avelumab DI= (actual dose)/(duration of avelumab treatment [weeks]/2) (mg/kg/2-week cycle)• Axitinib DI=(actual dose)/(duration of axitinib treatment [weeks])

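### The SAP does not say whether its shared 'date of initial dose' (the earlier of the two drugs' dates) applies to the per-drug durations; read literally, it lengthens the later drug's duration and lowers its dose intensity.

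*SAP*

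**What the plan says.** SAP 6.3 item 5, headed as the definition of the date of initial dose, says that when the two drugs are given for different durations, "the earlier of the two dates should be used as the date of the initial dose". It gives one date per patient and names no analysis to which it is confined.

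SAP 6.3 item 3 defines treatment duration separately for each drug. Avelumab duration is "Date of last dose – date of initial dose + 14"; axitinib duration has the same form with 1 in place of 14. Neither formula says whose initial dose is meant.

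SAP 8.3.2 then plans to "Tabulate the duration of treatment (months), DI, dosing status, and reason for interruption, dose change, or discontinuation of avelumab and axitinib". Avelumab dose intensity is the actual dose divided by half the avelumab duration in weeks; axitinib dose intensity is the actual dose divided by the axitinib duration in weeks.

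Two other parts of the SAP bear on the point. In the 6.3 time-to-event table, the PFS row allows for the drugs starting on different days ("if not on the same day, whichever occurs earlier"), while the two drug-specific TTF rows each start at that drug's own initiation. SAP 8.3.6 uses the date of initial dose to measure patient-level follow-up to death or last confirmed survival.

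**The concern.** Outside item 5, the term 'date of initial dose' occurs three times in the SAP: once in each of the two duration formulas and once in 8.3.6. Two of its three uses are therefore per-drug calculations, where a shared earliest date is unsuitable. A programmer who applies the defined term as written would start the later drug's exposure clock before that drug was given.

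Under that reading the error runs in one direction: longer duration and lower dose intensity for whichever drug began second. It is largest, in relative terms, in patients who stopped that drug early. It also gives one drug two different time origins in the same report, because its TTF starts at its own first dose while its treatment duration starts at the other drug's. Duration and dose intensity are the SAP's numerical summaries of how much of each drug was delivered, so a reader could take the shortfall for omitted or reduced doses.

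**Working it through.** The documents report no duration or dose intensity figure, so there is nothing to reproduce. The check applies the SAP's own formulas.

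**Inputs from the SAP**
- Avelumab duration = last dose − initial dose + 14 days; axitinib duration = last dose − initial dose + 1 day (6.3 item 3).
- Dose intensity = actual dose ÷ (weeks/2) for avelumab and actual dose ÷ weeks for axitinib (8.3.2).
- 1 week = 7 days; 1 month = 30.4375 days (6.2).
- Follow-up ends on 20 June 2021 and index dates run from 20 December 2019 to 20 December 2020, so potential follow-up is 182 to 548 days.

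**Assumptions (not in the documents)**
- Gap g between the two first doses: 7, 14 or 28 days.
- Number of avelumab cycles k: 3, 6, 12 or 24, with equal doses exactly 14 days apart. The longest case, 24 × 14 = 336 days, fits within the possible follow-up.

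**Step 1: the formula with the drug's own first dose.** With k doses 14 days apart, the last dose falls 14(k − 1) days after the first, so D = 14(k − 1) + 14 = 14k days. That is 2k weeks, and dose intensity = k doses ÷ (2k/2) = 1.000 dose per cycle. The formula is correct when the drug's own start date is used.

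**Step 2: the formula with the shared earlier date.** If avelumab starts g days after axitinib, the duration becomes 14k + g. The numerator is unchanged, so dose intensity is multiplied by 14k/(14k + g).

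| Cycles k | Own duration D (days) | Gap g (days) | Literal duration (days) | Relative dose intensity | Reduction |
|---|---|---|---|---|---|
| 3 | 42 | 14 | 56 | 42/56 = 0.750 | 25.0% |
| 6 | 84 | 7 | 91 | 84/91 = 0.923 | 7.7% |
| 6 | 84 | 14 | 98 | 84/98 = 0.857 | 14.3% |
| 6 | 84 | 28 | 112 | 84/112 = 0.750 | 25.0% |
| 12 | 168 | 14 | 182 | 168/182 = 0.923 | 7.7% |
| 24 | 336 | 14 | 350 | 336/350 = 0.960 | 4.0% |

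In months, the 6-cycle patient with a 14-day gap goes from 84/30.4375 = 2.76 to 98/30.4375 = 3.22. The 24-cycle patient goes from 336/30.4375 = 11.04 to 350/30.4375 = 11.50.

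**Step 3: axitinib.** If axitinib is the later drug, the same algebra gives D/(D + g). With D = 84 days and g = 14 days the factor is again 0.857.

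**Step 4: limits.** When g = 0 the factor is 1 for both drugs. The earlier-starting drug is never affected. With each drug's own dates, relative dose intensity for on-schedule dosing returns to 1.000 whatever the gap.

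**Step 5: from patient to cohort.** If a proportion p of patients had the same gap and the same D, mean relative dose intensity for the later drug would fall by p × g/(D + g). The documents give neither p nor g, so no cohort figure can be calculated.

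**The case against.** The strongest reply is that item 3 is already drug-specific. Its rows are labelled by drug, and the last dose in each formula carries no qualifier either, yet everyone would read it as that drug's last dose. The row label could supply the drug for the initial dose in the same way. Context helps this reading. SAP 8.3.6 needs one start date per patient, the combination TTF row does not say which drug's start applies, and the drug-specific TTF rows show that the authors separate drug-level from patient-level starts. Item 5 may have been written for those patient-level uses only.

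This stands as a plausible account of intent, and it rules out saying that the SAP will certainly produce wrong durations. It does not settle the text. The last dose has no competing definition elsewhere in the SAP; the initial dose does, two items further on in the same section and without a scope.

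Item 5 is also loosely worded: its condition is that the drugs are given for different durations, not that they start on different days. That weakens it as a strict global definition, and it is also a reason to rewrite it.

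A reader might infer that dose intensity in this study is understated by something like 14% or 25%. The documents do not support that. Both figures are per-patient illustrations under assumed gaps and cycle counts. The SAP foresees staggered starts, but nothing shows that they are common or long.

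**Conclusion.** The point holds in conditional form. The SAP gives an unscoped shared definition and then uses the defined term in formulas that need drug-specific dates. If followed literally, the later drug's duration is inflated by g and its dose intensity is multiplied by D/(D + g). For avelumab with an assumed 14-day gap, the reduction is 14.3% at 6 cycles and 4.0% at 24 cycles. For same-day starts it is zero. The study-level size is unknown, because neither the frequency nor the length of staggered starts is given.

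It would be wrong to infer that the efficacy results are compromised. The primary endpoint (baseline characteristics), PFS, objective response and the drug-specific TTF analyses do not use the affected formulas. The exposure is confined to the treatment duration and dose intensity tables in SAP 8.3.2. These are descriptive, and protocol 9.1.2 lists neither quantity among its avelumab or axitinib endpoints. The wording should be corrected because the change is cheap and the literal reading gives a wrong result, not because a conclusion of the study depends on it.

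**What to change.** - In SAP 6.3 item 3, define each duration from the first and last dose dates of that drug.
- In SAP 6.3 item 5, state that the shared earlier date applies only to combination or patient-level measures: combination TTF, PFS and the outcome table in 8.3.6.
- In the same item, make the condition that the two drugs have different start dates, in place of different durations.

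The cost is a few phrases in the SAP. No new data are needed, because protocol 9.3.5 and 9.3.6 already collect administration dates for each drug. If drug-specific dates were always intended, the edit only records that. It should be made before the tables are programmed and, since protocol 9.7.4 requires the SAP to be fixed before data lock, before the lock.

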#### **9.1.3.2. Real-world PFS**

Real-world PFS is defined as the following:

- Real-world PFS, defined as time from start of avelumab/axitinib treatment to date of first disease progression (as clinically assessed by local investigator based on radiology, laboratory evidence, pathology, or other assessments) or death due to any cause, whichever came first  
If there were no clinical records of death or disease progression, they were censored at the date of initiation of the next line of therapy for the patients undertaking two or more lines of therapy based on the record, or at their last visit date during the study period for the patients undertaking only one line of therapy based on the record.

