### **9.2.1. Inclusion criteria**

Patients must meet all of the following inclusion criteria to be eligible for inclusion in the study:

- 1) Diagnosed with mRCC based on the General Rule for Clinical and Pathological Studies on Renal Cell Carcinoma (4th Edition) before receiving avelumab plus axitinib as a first-line therapy;
- 2) Over 20 years of age at the time of mRCC diagnosis;
- 3) Start treatment with avelumab plus axitinib as a first-line therapy for mRCC from 20 December 2019 to 20 December 2020;
- 4) For patients who are still alive and have routine visits to the study site, evidence of a personally signed and dated informed consent document indicating that the patient has been informed of all pertinent aspects of the study. For patients who are still alive and had been transferred to another hospital, evidence that the patient has been informed of all pertinent aspects of the study and oral or written informed consent is obtained.
- 5) Deceased patients are also included for inclusion criteria 1-3.

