If there is no or unknown data of progressive disease (PD) in the [Progressive disease (PD) information] of the CRF, the date of diagnosis shall be the date of confirmation of the last progression-free survival.

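### SAP 6.3(6) ties the censoring of real-world PFS and all three TTF endpoints to an undefined diagnosis date that no reading makes sound

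*SAP*

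**What the plan says.** SAP 6.3 item 6 is the only place where the last progression-free date is defined. The condition is "If there is no or unknown data of progressive disease (PD) in the [Progressive disease (PD) information] of the CRF", and the consequence is that "the date of diagnosis shall be the date of confirmation of the last progression-free survival". The SAP does not define this diagnosis or name a CRF field for it.

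SAP 6.3 item 1 then uses the date for censoring. For real-world PFS the censoring date is "Date of last confirmation of progression-free survival or start of subsequent treatment (whichever occurs earlier". The three TTF rows (combination, avelumab, axitinib) share one wording: "Date of last confirmation of progression-free survival or date of last dose in case of efficacy stopping (whichever date occurs earlier".

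The protocol has a different rule for PFS. Section 9.1.3.2 states: "If there were no clinical records of death or disease progression, they were censored at the date of initiation of the next line of therapy" where the record shows two or more lines, "or at their last visit date during the study period for the patients undertaking only one line of therapy based on the record". Protocol 9.1.3.1 defines TTF by the end of treatment for any cause, including death, and does not mention progression. SAP section 9 declares no changes from the protocol.

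**The concern.** One sentence governs censoring in four secondary efficacy analyses (SAP 8.3.1.1, 8.3.1.2, 8.3.1.4 and 8.3.1.5). The only diagnosis that the documents place in time is that of the cancer, and it comes before treatment. A censoring date before the start date gives a time that a Kaplan-Meier analysis cannot use. The rule also handles unknown progression status exactly as it handles recorded absence of progression, and calls both a confirmation.

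At stake are the medians, the 3-monthly survival probabilities and the event rates for PFS and TTF. As the text stands, two programmers could derive different censoring dates and both claim to follow the SAP. Negative times would probably be noticed, but noticing them does not supply the right date. Someone would have to choose the rule after seeing data, although protocol 9.7.4 requires the SAP to be fixed before data lock.

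**Working it through.** The plan gives no sample-size or event calculation to reproduce. The check is a trace of the text under each possible reading, with an illustration of size.

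**Reading A: the cancer diagnosis.** Inclusion criterion 1 (protocol 9.2.1) requires the mRCC diagnosis "before receiving avelumab plus axitinib as a first-line therapy". Criterion 2 uses the word in the same sense ("Over 20 years of age at the time of mRCC diagnosis"), and the first IMDC item in protocol 9.3.2 counts time from diagnosis forward to systemic therapy. So diagnosis date − start date ≤ 0 for everyone. The table in item 1 takes the earlier of two dates, so the diagnosis date always wins. The reversed-date rule in SAP 6.1 covers only reversals produced by imputing partial dates and does not help. A patient censored at or before time zero is never in a risk set, so only patients with events shape the curve.

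Inputs for the illustration:
- Index window 20 December 2019 to 20 December 2020 and cut-off 20 June 2021 (protocol 9.1). Potential follow-up is 182 to 548 days; divided by 30.4375 (SAP 6.2), this is a = 5.98 to b = 18.00 months.
- About 70 patients (protocol 9.5).
- Median PFS 13.8 months, from the phase 3 trial cited in protocol section 7.
- Assumed: exponential PFS, uniform entry, no loss other than the cut-off.

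With L = ln 2 / 13.8 = 0.0502:

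Censored share = [exp(−La) − exp(−Lb)] / [L(b − a)] = (0.7406 − 0.4048) / (0.0502 × 12.02) = 0.556, or 38.9 of 70. Events: 31.1.

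Everyone has at least 5.98 months of potential follow-up. The events-only median m, if below that, therefore solves 1 − exp(−Lm) = 0.444 / 2 = 0.222, so m = −ln(0.778) / 0.0502 = 5.0 months. A simulation of 400,000 patients gives the same value.

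| Assumed true median (months) | Censored of 70 | Events | Median from events only (months) |
|---|---|---|---|
| 8 | 25.9 | 44.1 | 4.4 |
| 11.1 | 33.9 | 36.1 | 4.8 |
| 13.8 | 38.9 | 31.1 | 5.0 |
| 20 | 46.5 | 23.5 | 5.3 |

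At 13.8 months, simulated 12-month PFS is 8.5% against a true exp(−0.0502 × 12) = 54.7%, and the event rate is about 212 against 60 per 100 person-years. In 2,000 simulated studies of 70 patients, the events-only median had a 10th to 90th percentile range of 3.7 to 6.4 months.

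**Reading B: the date on which progression was diagnosed.** A patient without progression has no such date.

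**Reading C: a date on the CRF progression page.** This can be used for PFS when absence of progression is recorded, but three faults remain.
1. Unknown status counts as a confirmation.
2. The date differs from protocol 9.1.3.2. A patient with one line of therapy is censored at that page's date, not at the last visit. A patient with a later line is censored at whichever of that date and the next-line start is earlier, not at the next-line start.
3. Item 6 gives no date for a patient with recorded progression who is still on treatment, so that patient's TTF cannot be censored.

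The direction of bias for PFS under Reading C depends on figures that the documents do not give. Two illustrations at a true median of 13.8 months:
- If the page date lies up to 1.5 or 3 months (assumed) before the cut-off, the median falls to about 13.0 or 12.4 months.
- If 5%, 10% or 20% of patients (assumed) have unknown status and are carried to the cut-off as progression-free, the median rises to 14.9, 16.1 or not reached within 18 months. Twelve-month PFS becomes 57.0%, 59.3% or 63.9%.

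**The case against.** The strongest reply is that Reading A is not what the authors meant. The sentence sits under a heading about the last progression-free date and refers to a named CRF page; a date before treatment cannot be a last confirmation of anything. The wording is probably a translation slip. This stands: the 5-month median is what literal programming would produce, not a forecast of the study report. The CRF, which would settle the meaning, is not among the documents.

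It is also fair to say that the protocol itself censors patients who have no record of progression or death, without requiring documented absence of progression. Treating them as event-free is therefore the protocol's own convention. What is at fault is the date, and the label of confirmation for unknown status.

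A reader might infer that the rule biases PFS upward. The documents do not support this: the SAP does not say that unknown-status patients are carried to the cut-off, and censoring at an assessment before the last visit moves the median the other way.

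Finally, protocol 9.7 allows the SAP to modify the protocol's plans. That permits a different PFS rule, but SAP section 9 says there is none.

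**Conclusion.** The point holds. The censoring date for four secondary efficacy endpoints rests on an undefined term. Reading A gives times at or before zero, Reading B gives no date, and Reading C leaves an undeclared departure from the protocol, unknown status taken as confirmation, and a gap for TTF.

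The size depends on the reading. The literal worst case is about 39 of 70 patients losing all follow-up and a median near 5 months instead of 13.8, under exponential PFS, uniform entry and censoring only at the cut-off. On the likelier Reading C, the direction and size of bias are undetermined, because the assessment lag and the share of unknown status are not given.

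The consequence is limited to secondary, descriptive results. The primary endpoint (baseline characteristics) and all event dates are unaffected.

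**What to change.** 1. Delete the diagnosis date from SAP 6.3 item 6.
2. Censor real-world PFS as in protocol 9.1.3.2: at the start of the next line, otherwise at the last visit on or before 20 June 2021. If the last assessment documenting no progression is preferred, declare that change in SAP section 9.
3. For unknown progression status, use the protocol 9.1.3.2 date in the main analysis. Add a sensitivity analysis that censors at the last documented progression-free date, and state what applies when there is none.
4. Censor all three TTF endpoints at the last date known to be on treatment up to the cut-off, using the administration dates listed in protocol 9.3.5 and 9.3.6, not at a progression-free date.
5. Confirm that the CRF collects the last visit date, or the last assessment date if that is used. Protocol 9.3.3 lists only the start, progression and death dates, and 9.3.4 lists response categories without dates.

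The cost is a few sentences and table cells in SAP 6.3, the matching derivation code and one sensitivity analysis. Protocol 9.7 foresees an amendment only for major changes to the primary endpoint, so none should be needed. Whether new data are needed depends on item 5.

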7 GENERAL INFORMATION ON STATISTICAL ANALYSIS

7.1 Multiplicity adjustment

This will not be considered.

7.2 Summary statistics

Summary statistics for continuous variables will be calculated for observed and missing values, mean, median, standard deviation, minimum, maximum, first quartile, third quartile, etc.

Summary statistics for categorical variables will be calculated for frequency and proportion.

Other statistics, if calculated, will be described separately.

7.3 Significance level of the test

Unless otherwise specified, the significance level will be set to 5%. When confidence intervals are calculated, they should be two-sided with 95% confidence intervals.

7.4 Number of digits

In principle, the number of digits to be displayed shall be as shown below. This indicates the number of digits to be displayed in the output of results of the analysis; moreover, no rounding of values will be performed in the calculation process, unless otherwise specified.

Items	Number of digits
Number of patients, cases	Display as an integer
Mean, standard deviation, median, and interquartile range	Round off the last two significant digits of the target data, and display to the last digit.
Range	Display as significant digits of the target data.
Proportion (%)	Round off the second decimal place, and display to the first decimal place.

7.5 Interim analysis

No statistical interim analysis will be performed.

8 ANALYSIS METHODS

8.1 Subject disposition

Analysis set	Enrolled patients
Details of analysis	Develop a flow chart of the population to be analyzed (eligible patients) and ineligible patients. For ineligible patients, the number of patients who violated each selection criterion is also calculated.

